H_{A2} : The difference, between subjects treated with NOV03 and subjects treated with saline, in the mean CFB Dryness Score (VAS) at Day 57 $\neq 0$, with superiority claimed if the difference is less than 0 (NOV03 minus saline).

The study has been designed to have 95% power to reject both H_{01} and H_{02} assuming independence between the sign and symptom endpoint; positive correlation between these two endpoints would increase the overall power.

Estimated mean differences (common standard deviations) in CFB to Day 57 using an ANCOVA analysis with CFB to Day 57 as the response, baseline as a covariate and treatment as the fixed effect from NVU-002 are: -1.2 (2.5) for tCFS and -11 (26) for Dryness Score. Conservative estimates of -1.0 (2.8) for tCFS and -10 (28) for Dryness Score are used for sample size calculation.

Two hundred fifty (250) subjects (study eyes) per treatment group yields 97.9% power to reject H_{01} in favor of H_{A1} and conclude superiority of NOV03 over saline in the mean CFB tCFS score at Day 57 assuming a true difference (NOV03 minus saline) of -1.0, a common standard deviation of 2.8, and a two-sided alpha = 0.05. Two hundred fifty (250) subjects per treatment group yields 97.9% power to reject H_{02} in favor of H_{A2} and conclude superiority of NOV03 over saline in the mean CFB Dryness Score (VAS) at Day 57 assuming a true difference (NOV03 minus saline) of -10, a common standard deviation of 28, and a two-sided alpha = 0.05. Accounting for an assumed 10% subject discontinuation rate, approximately 560 subjects (280 subject each arm) will be

randomly assigned to trial treatment such that approximately 250 evaluable participants per arm complete the trial.

Therefore, assuming independence between tCFS score and Dryness Score (VAS), 250 FAS subjects per treatment group at Day 57 yields $97.9\% * 97.9\% = 95.8\%$ power to reject both H_{01} and H_{02} .

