4.4 Enrollment and Treatment Assignment

All treatment groups will be enrolled in parallel. Each subject will be assigned a unique subject number. All subject numbers will be assigned by Interactive Response System (IRS) in strict numerical sequence and no numbers will be skipped or omitted. If all eligibility criteria are met at Visits 0 and 1, each qualifying subject will then be randomized.

[figure not shown]
Site and Dryness Score <70 vs \geq 70 (VAS) at baseline (Visit 1) are used as a stratification factor in this trial. IRS will be used to account for the stratification factors while assigning the drug kit numbers at visits 1, 2 and 3. The subjects, investigators, Clinical Research Organization (CRO) personnel involved in conduct and monitoring of the trial and sponsor will be masked to IMP assignment.

Each subject will participate in the trial for approximately 10 weeks. The total duration of the trial from First Subject First Visit (FSFV) until Last Subject Last Visit (LSLV) is expected to be approximately 7 months.

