10.4.5 Primary Efficacy Analyses

The primary comparisons in this trial will be between NOV03 versus saline at Day 57 in the FAS with available data per subject using the following estimands:

- Population: Subjects with DED defined through enrollment criteria
- Endpoint:
 - CFB in tCFS in the study eye at Day 57
 - CFB of Dryness Score (VAS) at Day 57
- Intercurrent event:
 - Discontinuation of study medications is ignored. [treatment policy strategy]
 - Non-optimal compliance is ignored. [treatment policy strategy]

- Withdrawal due to any reason. Missing data not imputed. [hypothetical strategy]
- Population-level summary:
 - Difference in the mean CFB in tCFS in the study eye at Day 57 between NOV03 and saline.
 - Difference in the mean CFB of Dryness Score (VAS) at Day 57 between NOV03 and saline.

If the overall study discontinuation rate is $\geq 5\%$ then the primary analysis will be based on imputation methodology using the following estimands and the available data analyses will become robustness analyses.:

- Population: Subjects with DED defined through enrollment criteria
- Endpoint:
 - CFB in tCFS in the study eye at Day 57
 - CFB of Dryness Score (VAS) at Day 57
- Intercurrent event:
 - Discontinuation of study medications is ignored. [treatment policy strategy]
 - Non-optimal compliance is ignored. [treatment policy strategy]
 - Withdrawal due to lack of efficacy or adverse events. Baseline observation carried forward (BOCF) is used to impute missing data [hypothetical strategy].
 - Missing data without withdrawal or withdrawal due to reasons other than lack of efficacy or adverse events. Multiple imputations using randomized treatment-based Markov Chain Monte Carlo is used to impute missing data [hypothetical strategy].
- Population-level summary:
 - Difference in the mean CFB in tCFS in the study eye at Day 57 between NOV03 and saline.
 - Difference in the mean CFB in Dryness Score (VAS) at Day 57 between NOV03 and saline.

The primary comparison in this trial will be between NOV03 versus saline at Day 57. The primary efficacy endpoints (e.g. CFB in total corneal fluorescein staining [NEI scale] and Dryness Score) will be tested using hierarchical fixed sequence testing and summarized descriptively (n, mean, standard deviation, median, min, and max) and analyzed separately using an ANCOVA model with terms for baseline value, and treatment.

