- Treatment assignment method Subjects who meet all inclusion and exclusion criteria at Visits 0 and 1 will be randomized to a treatment group NOV03 (100% perfluorohexyloctane) or saline (0.6% sodium chloride solution) in a 1:1 ratio stratified by clinical site and dryness score <70 vs ≥ 70 (VAS) at baseline (Visit 1). Subjects who fail to qualify for the trial at screening may be rescreened (see Section 6.2).

An Interactive Response System (IRS) will be used to account for the stratification factors while assigning the drug kit numbers at Visits 1, 2 and 3. Each treatment group of this trial will consist of approximately 280 subjects, such that approximately 250 evaluable subjects per arm complete the trial, for an estimated total of 560 randomized subjects. Specifically, the treatments are defined as follows:

- Treatment 1: NOV03 (100% perfluorohexyloctane), 4 times daily (QID)
- Treatment 2: Saline (0.6% sodium chloride solution), QID
- Packaging and labeling The IMP will be labelled according to the legal requirements and packaged into individual subject kits, each containing 2 bottles of NOV03 or saline solution. In compliance with the Code of Federal Regulations 21 part 312, section 312.6, the labels for the IMP shall be comprised of:
 - Protocol number
 - Kit number
 - Investigational new drug statement
 - Storage conditions
 - Name and address of the sponsor
- **Trial configuration** This is a parallel trial design (NCI Preferred Term 'Parallel Study'). Subjects will be randomized to either NOV03 QID or saline QID in a 1:1 ratio. Subjects will self-administer one drop of masked investigation product in the lower cul-de-sac of each eye QID at approximately the same time e.g., morning, lunch time/midday, afternoon/early evening, and at bedtime. *Note*: if a dose is missed, the next dose should be administered on time.
- **Type of control used** This is a saline-controlled (NCI Preferred Term 'Placebo Control'), superiority trial.
- **Duration of the trial** The estimated trial duration is approximately 7 months, from first subject first visit to last subject last visit. An individual subject's participation will involve 5 visits over approximately a 10-week period, including screening. After the trial, subjects will be treated according to standard of care, at the discretion of the treating physician.

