6.5.7.3 Primary Efficacy Analyses

The primary comparisons in this trial will be between NOV03 versus saline at Day 57 in the FAS with available data per subject using the following estimands

- Endpoint:
 - CFB in tCFS in the study eye at Day 57
 - CFB of Dryness Score (VAS) at Day 57
- Intercurrent event:
 - Discontinuation of study medications is ignored. [treatment policy strategy]
 - Non-optimal compliance is ignored. [treatment policy strategy]
 - Withdrawal due to any reason. Missing data not imputed. [hypothetical strategy if overall study discontinuation rate is <5%]
- Population-level summary:
 - Difference in the mean CFB in tCFS in the study eye at Day 57 between NOV03 and saline
 - Difference in the mean CFB of Dryness Score (VAS) at Day 57 between NOV03 and saline

If the overall study discontinuation rate in the FAS is \geq 5% then the primary analysis will be based on imputation methodology using the following estimands:

• Endpoint:

Protocol Number: 904

- CFB in tCFS in the study eye at Day 57
- CFB of Dryness Score (VAS scale) at Day 57

• Intercurrent event:

- Discontinuation of study medications is ignored. [treatment policy strategy]
- Non-optimal compliance is ignored. [treatment policy strategy]
- Withdrawal due to lack of efficacy or adverse events: baseline observation carried forward (BOCF) is used to impute missing data [hypothetical strategy if overall study discontinuation rate ≥5%]
- Missing data without withdrawal or withdrawal due to reasons other than lack of efficacy or adverse events: multiple imputations using randomized treatment-based Markov Chain Monte Carlo (MCMC) is used to impute missing data [hypothetical strategy if overall study discontinuation rate ≥5%]
- Population-level summary:
 - Difference in the mean CFB in tCFS in the study eye at Day 57 between NOV03 and saline
 - Difference in the mean CFB of Dryness Score (VAS scale) at Day 57 between NOV03 and saline

The primary comparison in this trial will be between NOV03 versus saline at Day 57. The primary efficacy endpoints (e.g. CFB in total corneal fluorescein staining [NEI scale] and Dryness Score) will be tested using hierarchical fixed sequence testing and summarized descriptively (n, mean, standard deviation, median, min, and max) and analyzed separately using an ANCOVA model with terms for baseline value, and treatment.

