Least squares mean for each treatment group and for the difference between treatment groups will be presented from each model together with two-sided p-values (used for primary inference) and 95% confidence intervals.

Sample SAS ANCOVA code:

```
PROC GLM DATA=INDATA;
CLASS <TREATMENT>;
MODEL <ENDPOINT>=<TREATMENT> <BASELINE>;
LSMEANS <TREATMENT> / CL ALPHA=0.05;
LSMEANS <TREATMENT> / PDIFF CL ALPHA=0.05;
RUN;
```

Additional robustness analyses will include repeating the primary analysis on the PPS; the FAS imputing missing data using last observation carried forward (LOCF); the FAS imputing missing data using MCMC multiple imputation methodology under different assumptions of missingness (at random and not at random) each using 30 imputed values.

Sample SAS MCMC MI (missing at random):

```
PROC MI DATA=INDATA SEED=97656 OUT=OUTDATA MINIMUM=0 MAXIMUM=3 ROUND=1 NIMPUTE=30;
MCMC INITIAL=EM;
```

```
BY <TREATMENT>;
VAR <BASELINE> <PARAMETER>;
```

Where <PARAMETER> has 5 levels and refers to the CFS for each region (inferior, superior, central, temporal, and nasal).

Sample SAS MCMC MI (not missing at random):

```
PROC MI DATA=INDATA SEED=36797 OUT=MDATA MINIMUM=0 MAXIMUM=3 ROUND=1
NIMPUTE=30;
MCMC IMPUTE=MONOTONE;
VAR <BASELINE> <PARAMETER>;
RUN;

PROC MI DATA=MDATA SEED=38549 OUT=OUTDATA2 MINIMUM=. 0 0 MAXIMUM=. 3 3
ROUND=. 1 1;
CLASS <TREATMENT>;
MONOTONE REG(<PARAMETER>=<BASELINE> / DETAILS);
MNAR MODEL(<PARAMETER> / MODELOBS=(<TREATMENT>='Saline'));
VAR <TREATMENT> <BASELINE> <PARAMETER>;
RUN;
```

Where <PARAMETER> has 5 levels and refers to the CFS for each region (inferior, superior, central, temporal, and nasal).

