6.5.7.6 Sensitivity Analyses

6.5.7.6.1 Sensitivity Analyses for Primary Efficacy Endpoints

Two-sample t-tests (equal variance assumed), Wilcoxon rank sum tests and mixed-effect repeated measures analysis comparing treatment groups will be performed as sensitivity analyses. The mixed-effect repeated measures model will include treatment, baseline value, visit, and the interaction between treatment and visit as fixed effects, and subject as a random effect. An unstructured covariance matrix will initially be used to model the covariance among repeated measures; however, if the model fails to converge using this covariance structure, either heterogeneous TOEPLITZ, homogeneous TOEPLITZ, or compound symmetry will be implemented according to the Akaike information criterion with a correction for finite sample sizes (AICc).

Sample SAS two-sample t-test code:

```
PROC TTEST DATA=INDATA;
  CLASS <TREATMENT>;
  VAR <ENDPOINT>;
RUN;
```

Sample SAS Wilcoxon rank sum test code:

```
PROC NPAR1WAY DATA=INDATA WILCOXON;
  CLASS <TREATMENT>;
  VAR <ENDPOINT>;
RUN;
```

Sample SAS mixed-effect repeated measures analysis code:

```
PROC MIXED DATA=INDATA;

CLASS <TREATMENT> <VISIT> <SUBJECT>;

MODEL <ENDPOINT>=<TREATMENT> <VISIT> <TREATMENT>*<VISIT> <BASELINE>;

REPEATED <VISIT> / SUBJECT=<SUBJECT> TYPE=UN;

RANDOM <SUBJECT>;

ESTIMATE 'NOV03-SALINE' <TREATMENT> -1 1 / ALPHA=0.05 CL;

RUN;
```

Where 'Saline' is <TREATMENT>=0 and 'NOV03' is <TREATMENT>=1.

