6.5.8.5 Adjustment for Covariates

The primary endpoints are CFB in total corneal fluorescein staining (NEI scale) at Day 57 and CFB of Dryness Score (VAS) at Day 57. The two primary endpoints will be analyzed separately using an ANCOVA model with baseline measurement as a numeric covariate and treatment as the main effect.

Subject randomization is stratified by clinical site and dryness score $<70 \text{ vs} \ge 70 \text{ (VAS)}$ at baseline (Visit 1). The analyses will not be adjusted for the stratification factors.

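### Randomisation is stratified by site and baseline dryness, but the analyses leave both factors out and give up a small, nearly free gain in precision

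*SAP*

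**What the plan says.** Protocol 4.4 says that site and the Dryness Score split at 70 "at baseline (Visit 1) are used as a stratification factor in this trial". SAP section 4 repeats this: subjects are randomised "in a 1:1 ratio stratified by clinical site and dryness score <70 vs" 70 or above. SAP 6.5.8.5 then states that "The analyses will not be adjusted for the stratification factors".

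The models agree with that statement.

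- **Primary ANCOVA.** Protocol 10.4.5 has the endpoints "analyzed separately using an ANCOVA model with terms for baseline value, and treatment". The SAP 6.5.7.3 code is "MODEL <ENDPOINT>=<TREATMENT> <BASELINE>".
- **Mixed model (sensitivity).** The SAP 6.5.7.6.1 code is "MODEL <ENDPOINT>=<TREATMENT> <VISIT> <TREATMENT>*<VISIT> <BASELINE>", with no site or stratum term.
- **Logistic model.** SAP 6.5.7.4.2 adjusts for baseline tCFS only.
- **Site.** SAP 6.5.8.8 plans no formal analysis by site.

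If the discontinuation rate is 5% or more, the primary analysis changes. SAP 6.5.7.3 then uses baseline carried forward for withdrawals due to lack of efficacy or adverse events. For other missing data, "multiple imputations using randomized treatment-based Markov Chain Monte Carlo (MCMC) is used to impute missing data". Neither factor is named in the imputation.

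**The concern.** Stratified randomisation balances the arms on the chosen factors. If those factors predict outcome, the balance reduces the true variance of the treatment contrast. A model without them leaves their variation in the residual, so it reports more uncertainty than there is, and its test runs below the nominal 5%.

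The gap differs by endpoint. The Dryness Score ANCOVAs already carry numeric baseline dryness, so they lack essentially only site. The tCFS, central staining and VAS burning/stinging models lack both factors.

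What is at stake is precision, not validity. It matters most for the four secondary endpoints tested in sequence: no effect size or power is stated for them, and one failure ends inference on those below it.

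**Working it through.** **Inputs from the documents** (Protocol 10.3 and 4.1, SAP 6.5.10): tCFS difference −1.0, SD 2.8; Dryness Score difference −10, SD 28; two-sided alpha 0.05; 250 evaluable and 280 randomised per arm; 10% discontinuation; about 35 sites. That is 560/(35 × 2) = 8 randomised subjects per stratum.

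**Assumed, because the documents do not give them:** the share R² of baseline-adjusted residual variance explained by site and stratum (0 to 15%), permuted blocks of 4, uneven site sizes (gamma, CV 0.6) and random dropout.

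**1. The plan's own figure.** SE = 2.8 × √(2/250) = 0.2504. Power = Φ(1.0/0.2504 − 1.96) = 97.9%. The Dryness Score has the same effect-to-SD ratio, so also 97.9%. Jointly, 0.979² = 95.8%. Both stated figures reproduce. The planning SDs were set from an NVU-002 ANCOVA with "baseline as a covariate and treatment as the fixed effect from NVU-002", the same two terms, so the sample size fits the two-term model.

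**2. Two-term model.** Let q be the site imbalance left after blocking, relative to simple randomisation. In 1,500 simulated designs, q = 0.20.

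- True variance = reported variance × [1 − R²(1 − q)]
- SE overstatement = 1/√[1 − R²(1 − q)] − 1
- True alpha = 2[1 − Φ(1.96/√(1 − R²(1 − q)))]

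At R² = 10%: 1 − 0.10 × 0.80 = 0.92. The overstatement is 1/√0.92 − 1 = 4.3% and true alpha is 4.1%. Power is Φ[(1.0 − 1.96 × 0.2504)/(0.2504 × √0.92)] = Φ(2.12) = 98.3%. With perfect balance (q = 0) the overstatement would be 5.4%.

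**3. Adjusted model.** Reported variance = two-term variance × v(1 − R²), where v is the cost of the extra terms. v = 1.018 with 35 unpooled sites; v = 1.010 with sites under 10 randomised subjects pooled (about 26 groups); v = 1.0004 for the dryness term alone. Unpooled at R² = 10%: SE = 0.2504 × √(1.018 × 0.90) = 0.2397, and power = Φ(1/0.2397 − 1.965) = 98.6%. The pooled rows below come from the simulated designs, because the pooled group leaves a little site variation unexplained.

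| R² | 0% | 5% | 10% | 15% |
|---|---|---|---|---|
| Two-term SE overstated by | 0% | 2.1% | 4.3% | 6.6% |
| Two-term true alpha | 5.0% | 4.5% | 4.1% | 3.7% |
| tCFS power, two-term | 97.9% | 98.1% | 98.3% | 98.5% |
| tCFS power, unpooled sites | 97.7% | 98.2% | 98.6% | 99.0% |
| tCFS power, pooled sites | 97.8% | 98.2% | 98.6% | 99.0% |
| tCFS 95% CI half-width, two-term | 0.491 | 0.491 | 0.491 | 0.491 |
| tCFS 95% CI half-width, pooled | 0.495 | 0.483 | 0.472 | 0.460 |
| Power at assumed 0.25 SD effect, two-term | 79.8% | 80.3% | 80.8% | 81.3% |
| Power at assumed 0.25 SD effect, pooled | 79.3% | 81.1% | 83.0% | 84.9% |

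**4. Break-even.** Adjustment starts to gain power at R² of about 3% unpooled and about 2.0 to 2.4% pooled (1.7 to 2.8% for block sizes 2 to 8).

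**5. If the NVU-002 estimates hold** (−1.2, SD 2.5; −11, SD 26), two-term power is already 99.97% and 99.7%, so adjustment adds nothing useful for the primaries.

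**6. Branch with discontinuation of 5% or more.** With 10% missing at random, imputation by arm on baseline only, and site added to the ANCOVA but not to the imputation, the reported SE changes by +0.2/−1.4/−3.0/−4.6% at R² = 0/5/10/15%. Null rejection at R² = 0/10/15% is 5.1/5.0/4.7% adjusted against 5.2/4.3/4.0% two-term. The baseline-carried-forward part was not simulated.

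**7. Cross-check.** A separate simulation (2,000 trials per setting, Monte Carlo error about 0.5 points on a 5% rate) agrees. With no site effect, adjustment moves the mean tCFS SE from 0.251 to 0.253. With a 10% site share, the two-term SE averages 0.250 against an empirical SD of 0.235 to 0.245, and the null rejection rate is 3.6 to 3.9% across the two primary endpoints.

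**The case against.** The case for leaving the plan alone is reasonable. The protocol and SAP give the same two-term model, the exclusion is stated openly, and the sample size was built on that model. The error is conservative and primary power moves by half a point or less.

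R², block size and site sizes are all assumed. The model includes baseline, and Protocol 8.4.1 prefers the same assessor for each subject, so much of any site grading effect may cancel. Below an R² of about 2 to 3%, adjustment loses a little power. The 0.25 SD effect is only an illustration. The plan's own 10% discontinuation would trigger the imputation branch, where the gain is smaller. Changing a confirmatory model also has an administrative cost.

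All of this stands, and it limits the point to a minor one. It does not remove it. The loss if the factors explain nothing is bounded at about 0.5% of the SE with pooling, and no specified efficacy analysis, primary or sensitivity, reflects the full randomisation scheme.

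**Conclusion.** The point holds as a low-priority improvement. Omitting the stratification factors never makes the analysis anti-conservative. If they explain 5 to 15% of residual variance, the two-term model overstates the SE by about 2 to 7%, and pooled adjustment narrows the tCFS interval by about 1.6 to 6.3% (0.483 to 0.460 against 0.491). The practical value is near zero for the primaries at the planned effect. For an endpoint with about 80% power it is about 1 to 4 points. Confidence is moderate: direction and cost are firm, but the gain depends on an R² that the documents do not give, and the benefit of the dryness term alone was not separated from that of site.

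**What to change.** Amend SAP 6.5.8.5 before database lock and unmasking, by the amendment route in SAP section 4.

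1. Add the dryness stratum or numeric baseline dryness (1 df) to the tCFS, central staining and VAS burning/stinging models.
2. Add site to the primary and secondary ANCOVA and mixed models. Pool small sites by a rule fixed on masked counts, for example all sites with fewer than 10 randomised subjects in one group; the sponsor should set the threshold.
3. Keep the two-term ANCOVA as a sensitivity analysis.
4. Record the departure from Protocol 10.4.5 in SAP 6.6, which now lists no changes, and in the protocol if required.
5. In the branch for discontinuation of 5% or more, fit the adjusted ANCOVA to each imputed dataset and add baseline dryness to the imputation model. Do not require unpooled site indicators in by-arm imputation: 280/35 is only about 8 subjects per site per arm.

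No new data are needed; SAP 6.5.1 already tabulates the analysis populations by both factors. If site explains nothing, the SE is about 0.5% wider with pooling (about 25 df), or about 0.9% wider with 35 unpooled sites (about 34 df). The dryness term alone costs about 0.02%. If the sponsor prefers not to alter the primary test, the adjusted model can be pre-specified as a sensitivity analysis, with the reason for excluding the factors stated.

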6.5.8.6 Handling of Dropouts or Missing Data

Missing data will be handled as follows. Missing data for other data points not covered below will be left as missing. Nominal visits for subjects who withdraw will be handled per Section 6.5.8.2.

6.5.8.6.1 Imputation Method for Efficacy Endpoints

The primary analysis will be completed on the FAS with available data per subject, assuming the overall study discontinuation rate is \leq 5%. If the overall study discontinuation rate is \geq 5% then the primary analysis will be based on the primary imputation methodology as defined Section 6.5.7.3 and the available data analyses will become robustness analyses.

Additionally, robustness analyses will include repeating the primary analysis on the per protocol set (PPS); the FAS imputing missing data using last observation carried forward (LOCF); the FAS imputing missing data using Markov Chain Monte Carlo (MCMC) multiple imputation methodology under different assumptions of missingness (at random and not at random) each using 30 imputed values.

